# A pairwise randomized study on implementation of guidelines and evidence based treatments of psychoses

# 1. Relevance relative to the call for proposals

- The project is targeting patients with severe mental illness and is partly health services research.
- It is "patient-near" as it addresses service delivery to patients (service users) and collects data on outcome in relation to implementation. Service users are involved in all stages in the project.
- It is relevant for the health services as it will give new knowledge on current implementation of clinical guidelines, and on how implementation on evidence based treatments can be improved.
- The project includes mental health clinics from six health authorities in three health regions of Norway, including three university hospitals.

# 2. Aspects relating to the research project

The objectives are described in the grant application form.

# 2.1. Background and status of knowledge

Persons with severe mental illness are among the key target groups for the mental health services, and it is of major importance to know whether the mental health services succeed in helping this group. The mental health services in Norway are giving services to 165 000 adults during a year, and 13 000 of these (8 %) have psychoses (F20-29 in ICD-10). Ten percent of the total patient population uses 80 % of the resources, and 28 % of these are persons with psychoses, indicating that many of these have great needs for comprehensive services [1]. Child and adolescent mental health services additionally meet 400 adolescents with psychoses during a year.

#### Evidence based treatments and clinical guidelines

Several treatment approaches and specific interventions have been developed for psychoses, and there is now research based evidence for several for these that they are effective. These include pharmacological treatments (such as antipsychotic drugs) and psychological therapies (such as cognitive behavioral therapy, work with families, psycho-education, supported employment, illness management and recovery, and integrated treatment of psychosis and substance abuse).

During the last two decades an increasing number of clinical guidelines have been developed, based on reviews and meta-analyses of research. The aim has been to contribute to closing the gap between research evidence (what is known) and routine clinical practice (what is done).

In spite of these developments and intentions to improve the services by practicing guidelines, the extent to which guidelines are implemented in everyday routine practice in Norway and elsewhere is largely unknown. We know even less whether implementation of clinical guidelines actually improves patient outcome. The few implementation studies reported in a recent Cochrane review [2] and other reviews [3] indicate that guideline implementation is typically fragmented or lacking, and that improved patient outcome may be limited even when guideline implementation occurs.

There may be several reasons for this. One is that there is a roadblock to translate knowledge and new methods from optimized efficacy trials into everyday clinical practice [4]. The pathway from evidence generation to evidence synthesis and guideline development is well developed, but the pathway from evidence-based guidelines to evidence-based practice is much less developed. In efficacy studies clinicians may have been selected and especially skilled or motivated, and patient groups in such trials are often selected based on several exclusion criteria. But in everyday practice non-selected clinicians are supposed to change their practice to implement evidence based treatments with unselected patients with various comorbidity and additional problems that were excluded in the trials which the guidelines are based on.

#### Fidelity measures for implementation of evidence based treatments for psychoses

Fidelity scales have been developed for several of these, providing objective data on whether a clinical team or program have implemented key components of the evidence-based model for a treatment or service delivery. "The rationale for using fidelity scales to guide practice is based on the working hypothesis that programs successfully replicating the core principles and procedures of

the program models rigorously evaluated in controlled studies will achieve similar outcomes as these earlier studies" [5].

The US National Evidence-Based Practices project (US NEBP) made a major contribution to developing strategies and fidelity measures for research on implementation of evidence based treatments for this group. Five evidence based treatments (Assertive Community Treatment, Family Psycho-education, Integrated Dual Disorder Treatment, Illness Management and Recovery, Supported Employment/IPS) were chosen, and 53 CMHCs in 8 states each implemented one of these. Implementation was successful in various degrees across sites and types of evidence based treatment. US NEBP developed several fidelity scales, and designed and studies a comprehensive implementation support program [6-9].

Some European studies on evidence-based treatments for schizophrenia have developed indicators based on guidelines, but these have not been developed as fidelity scales [10, 11].

#### Implementation support programs

Research has shown that several strategies need to be combined both on the system level and for clinicians in order to achieve a successful implementation of a new practice. Frameworks for strategies are emerging to structure such combined approaches [12-15]. Strategies also define what is important in various stages in the implementation process and in relation to different target groups [16-20]. It is important to engage leaders on all levels to be involved in the decisions and process of implementation throughout the whole process. In order to change clinical practice, clinicians must understand and agree on the need to change practice, and receive supervision and feedback frequently over some time by supervisors taking part in small group discussions at the local site and communicating results from fidelity assessments and other relevant measures.

According to a recent review of studies on implementation in mental health, US NEBP had the implementation program with the most comprehensive list of elements and activities [21]. Based on a review of the implementation literature the elements included in the US NEBP were toolkits with a practice manual and other tools to implement the practice, a trainer who made frequent onsite visits to the agency implementing the practice, a fidelity review process with feedback, a "kickoff" to build enthusiasm, initial training for the practitioners, consultations and technical assistance to the agency leadership, and consultation and technical assistance to the governmental authority responsible for mental health services. It was also emphasized that the implementation support must be reasonably intensive during the first months, must be sensitive to site-specific conditions, and helpful to implementers through three phases of implementation: building momentum for change, making the changes, and reinforcing the changes. The toolkit contained workbooks, research articles, introductory and instructional videotapes, PowerPoint lectures and the fidelity scales.

#### Situation in Norway and collaborating partners in the project

The Norwegian national guidelines on assessment and treatment of persons with psychoses (2013) give 74 different recommendations for assessment and treatment. Each of these is rated regarding level of evidence and importance. We do not know to which extent these are implemented.

The mental health clinics of six health authorities (including three university hospitals) are partners in the project, representing three of the health regions in Norway and serving a total population of 1,9 million (38 % of Norway's population). Altogether they have 30 CMHCs (with outpatient clinics, day units, mobile teams, and inpatient wards). Each serves a specific area and population.

Health authorities with mental health clinics that are collaborating partners in the project

Treath dutionaes with mental nearth chines that are condorating partites in the project				
Health	Mental health clinics from these health	CMHCs	Population	Patients
Region	authorities are partners in the project		in area	F20-29*
South-East	Akershus University Hospital	4	500 000	1 400
	The Hospital Innlandet	5	400 000	1 120
	Sørlandet Hospital	4	290 000	810
West	Stavanger University Hospital	5	330 000	920
	Health Fonna	4	170 000	480
North	University Hospital of Northern Norway	8	230 000	640

Total 30   1920 000
---------------------

\*) Estimated number of patients 16+ years old with F20-29 (ICD-10) seen during one year.

#### 2.2. Approaches, hypotheses and choice of method

#### 2.2.1.Research questions

- 1. What is the current level of implementation in the mental health services of selected core elements in the national clinical guidelines for treatment of persons with psychoses?
- 2. Is implementation of the selected core guidelines improved by a comprehensive implementation support program compared with no such support?
- 3. Does implementation of selected core guidelines improve patient care pathway, patient outcome and satisfaction of patients and their families?

# 2.2.2. Hypotheses

- 1. Current implementation of evidence based approaches and treatments are low.
- 2. A comprehensive implementation program for an evidence based treatment gives significant increase in implementation of the treatment compared to no such specific program.
- 3. Higher implementation of core clinical guidelines is associated with better patient care pathways, patient outcome and higher satisfaction of patients and their families.

# 2.2.3.Design and overview of the Implementation Study and the Patient Outcome Sub-study Implementation Study

The design of the main study is a randomized paired design to answer research question 2. The unit of analysis for the implementation study is the CMHC, and the primary outcome measure is fidelity to recommendations/treatment packages. Each of the 30 CMHCs chooses two of packages that they will implement. For each center we randomize implementation support to one package and no support to the other one. 30 pairs of packages are randomized for implementation support or not.

We have chosen the CMHCs because they are the clinical units giving the whole range of outpatient and outreach services over time for the population in a local area, including for persons with psychosis. Other departments serving patients with psychosis may also get implementation support for treatment packages, but they will not be included in the randomized design for CMHCs.

We have selected four treatment packaged covering core recommendations in the Norwegian guidelines (see 2.2.4 below). A survey among the CMHCs and departments in May 2015 showed adequate interest for the four chosen treatment packages. The survey before the final selection of treatment packages was done according to our plan to wait with the final decision on design A or B is supported by the advices given by the Medical Research Council in UK for research on complex interventions [22].

The level of implementation of two chosen packages at each CMHC/department is assessed with fidelity scales at baseline before implementation and after 6, 12 and 18 months.

The fidelity measured at baseline (before the start of implementation support) will show the current implementation of the treatment packages across centers (research question 1).

Necessary number of CMHCs: Based on data from the US NEBP project, we have calculated that we need 8 CMHCs in each branch to show that implementation support for a treatment package gives a significant increase in fidelity compared to baseline or low fidelity. In their project fidelity assessors reliably rated EBP fidelity on 5-points fidelity scales (1 = poor fidelity...5 = high fidelity) [8]. Average fidelity scores across all five EBPs and 51 sites receiving implementation support were 2.28 (SD 0.95) at baseline 3.76 (SD 0.78) after 12 months (effect size 1.70). Our calculation is based on their data and 5% two-tailed significance and 90% power. If the differences are smaller in our study, we will need a larger sample. However, it is unlikely to have a large increase in fidelity without implementation support [23].

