#### Treatment packages for randomization

We study the implementation of only four treatment packages in our project in order to make it feasible for the services to have a limited number of models to focus on, and to obtain the necessary power for the statistical analyses (see calculations under 2.2.3 above).

Our selection of treatment packages has been based on these criteria: (a) They cover one or more recommendation with high evidence (1a/1b) and/or high importance (A) in the Norwegian guidelines, (b) they are considered by the participating collaborators to be among core elements in the services for persons with psychosis, (c) there are available fidelity scales that may be used or potential measures that may be adapted, (d) they may be relevant for most patients with psychosis, (e) the required competence is available or within reach by training in the collaborating health authorities, (f) they are feasible for the services, and (g) the related recommendations refer to treatments and not assessments, as we are focusing on treatments. Below we briefly describe the selected packages, also showing which recommendation (Rxx) each covers.

Antipsychotic medication: Specific elements include using antipsychotics in treatment of psychosis, limiting polypharmacy, avoiding high doses and fast increase of doses, differentiating dosage in different phases and situation, and trying clozapine if two other antipsychotics have been tried without effect. Recently developed fidelity measures (MedMAP) are adapted to cover the core recommendations on antipsychotic medication in the guidelines [24-26] (R43-60). Efforts to improve adherence and observe side effects are also defined and included.

Family interventions: Collaboration with carers/family, family psycho-education and meeting children of the patient are considered evidence based treatments. There are available fidelity scales for measuring family support and psycho-education [27]. We clarify the model and include a measure on following up children of patients. This treatment package covers six recommendations in the guidelines (R4, R28-32).

Care for somatic health: The need for attention to somatic health is great due to the documented higher morbidity and mortality of persons with schizophrenia and related psychoses. Physical activity is also important for somatic health. This treatment package covers three recommendations

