# 2.2.8.Plan for data analyses

# Analysis in Study of implementation of guidelines (research questions 1 and 2)

To answer Research Question 1, we will examine baseline fidelity scores for the four treatment packages, using the benchmark of 4.0 as adequate fidelity. We will calculate the percentage of sites achieving benchmark fidelity (4.0) at baseline. We will also analyze the distribution of fidelity scores and explore contributing factors the reasons, including any barriers that may be addressed.

Analyses to answer Research Question 2 will partly depend on the final decision on design (see 2.2.3 above). First, we will compare the experimental and control conditions on fidelity across time, controlling for baseline and ignoring the content of package. This analysis will consist of 30 pairs of sites, measured 4 points in time. Baseline scores will be used as covariates. We consider various ANONVA analyses. Second, for each package we will compare all experimental sites to all control sites. The number of observation in this analysis will depend on how many CMHCs choose each of the EBPs. Baseline scores will be used as covariates. Third, we will examine within-group changes over time for each package receiving implementation support, calculating effect size and determining percentage of sites achieving benchmark fidelity (4.0) at each time period.

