#### 2.3.4.Plan of progress

Preparations of training material and design of forms for data collection are finished in November 2015, and training of implementation trainers and researchers is done in January 2016. The CMHC/department chooses two treatment packages in November/December 2015. Baseline assessment of implementation of the selected treatments is done in February 2016, and pairwise randomization of implementation support is done right after the baseline assessment of fidelity.

Inclusion of patients for the patients sub-study starts 1 March 2016 with a 6 months inclusion period. Intensive implementation support also start in March and is given for 6 months, and then regular implementation support is given for 12 months. Implementation assessment is done again 6, 12 and 18 months after the start of implementation support.

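### Does scoring only the two packages each CMHC chose leave research question 1 without a valid answer?

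*Protocol*

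**What the plan says.** Section 2.2.3 sets the design: "Each of the 30 CMHCs chooses two of packages that they will implement". Section 2.2.4 gives the menu: "We study the implementation of only four treatment packages in our project". On measurement, section 2.2.3 says: "The level of implementation of two chosen packages at each CMHC/department is assessed with fidelity scales at baseline". The next statement on baseline is that these scores "will show the current implementation of the treatment packages across centers (research question 1".

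Section 2.3.4 fixes the order. A centre "chooses two treatment packages in November/December 2015", and then "Baseline assessment of implementation of the selected treatments is done in February 2016". Section 2.2.6 places baseline in January 2016 instead, but on either date the choice comes first.

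For research question 1, section 2.2.8 says: "we will examine baseline fidelity scores for the four treatment packages, using the benchmark of 4.0 as adequate fidelity". It continues: "We will calculate the percentage of sites achieving benchmark fidelity (4.0) at baseline". It adds a look at the distribution of scores and at contributing factors. It plans no test and no estimate for all 30 centres.

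Research question 1 (section 2.2.1) asks about the mental health services generally, and hypothesis 1 (section 2.2.2) holds that implementation is low. Neither mentions which centres chose which package.

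**The concern.** The centres decide for themselves where fidelity is observed. A centre already strong on a package might see little reason to choose it, or might prefer it for that very reason. The protocol does not say whether choice is related to current practice. If it is, the mean fidelity of a package among choosers differs from its mean over all 30 centres, and so does the share at 4.0.

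The wording for research question 1 carries no reminder of this. Section 2.2.8 notes that numbers depend on how many centres pick each package, but only for the per-package comparison under research question 2. Two other sources bear on unchosen packages: the May 2015 interest ratings (section 2.2.4) and the clinician form on treatment content (section 2.2.6). Neither yields a fidelity score, and section 2.2.8 uses neither for research question 1.

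At stake is how far a descriptive result reaches. It could be reported as a package's level across all the participating centres when it comes from about half of them.

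**Working it through.** **Inputs from the protocol.** 30 CMHCs (the table in section 2.1 adds up: 4 + 5 + 4 + 5 + 4 + 8 = 30); 2 packages chosen per CMHC (section 2.2.3); 4 packages available (section 2.2.4); 5-point fidelity scale and an earlier project's baseline mean of 2.28 (section 2.2.3); benchmark 4.0 (section 2.2.8). The protocol gives no sample size or precision for research question 1, so there is no figure of its own to reproduce here. Its requirement of 8 CMHCs per branch concerns the effect of implementation support.

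**Coverage.** Observed combinations: 30 × 2 = 60. Possible combinations: 30 × 4 = 120. Average per package: 60 / 4 = 15 CMHCs. The actual split is not given. The count covers CMHCs only; sections 2.2.3 and 2.3.4 also speak of departments, which may add scores.

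**Logical limits on the all-centre share at 4.0.** With n CMHCs choosing a package and k of them at benchmark, the share over 30 lies between k/30 (no non-chooser at benchmark) and (k + 30 − n)/30 (every non-chooser at benchmark). Assumed: n from 10 to 20, and 20% of choosers at benchmark.

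| n | k | Lower limit | Upper limit |
|---|---|---|---|
| 10 | 2 | 2/30 = 7% | 22/30 = 73% |
| 15 | 3 | 3/30 = 10% | 18/30 = 60% |
| 20 | 4 | 4/30 = 13% | 14/30 = 47% |

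**Shift in the mean.** If non-choosers differ from choosers by d points on average, the all-centre mean differs from the chooser mean by d × (30 − n)/30: 0.67d for n = 10, 0.50d for n = 15, 0.33d for n = 20. The protocol gives neither size nor sign for d.

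**Limits on the mean.** Assume choosers average 2.28, and let every non-chooser score 1 or 5.

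- n = 10: (22.8 + 20)/30 = 1.43 to (22.8 + 100)/30 = 4.09
- n = 15: (34.2 + 15)/30 = 1.64 to (34.2 + 75)/30 = 3.64
- n = 20: (45.6 + 10)/30 = 1.85 to (45.6 + 50)/30 = 3.19

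The upper limit passes 4.0 only for n = 10, and only if all 20 unobserved centres have perfect fidelity. These are outer limits, not plausible values.

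**The text side by side.** In section 2.2.3 the statement about research question 1 refers back to the baseline scores just described, which are those of the two chosen packages. Section 2.3.4 says the same of the selected treatments. All 30 CMHCs contribute and, unless nobody picks a package, all four packages are scored. The statement is therefore true of the data collected. In section 2.2.8 a per-package percentage needs a score for each site counted, so its denominator is the set of sites assessed on that package.

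**The case for a change.** The best case for a change runs as follows. Section 1 offers new knowledge of current guideline implementation as a reason for the project, and section 2.1 says that its extent is unknown. Research question 1 is thus a stated deliverable. The centres were not sampled; they chose what they would implement. The authors knew that choice drives the numbers, since they say so under research question 2. A statistical analysis plan can define a denominator but cannot supply scores that were never collected. One clause would remove the ambiguity at no cost.

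Part of this stands. The result for each package does apply to the centres that chose it, and no later document can widen it. The workload remark in section 2.2.7 about assessing more than two packages does not amount to a plan to score unchosen ones.

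It does not show an error in the protocol, however. The limit is already stated twice, and broad research questions are normally narrowed by the methods that follow them. Labelling the analysed set and giving its size is routine work for an analysis plan or report, and the analysis plan is not at hand here. The only step that would add information is scoring all four packages everywhere. That would double the baseline package scores from 60 to 120, at an effort that section 2.2.7 already counts in days per researcher, for packages outside the randomized comparison.

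**Conclusion.** No change is needed. The limitation is real but disclosed: 60 of 120 combinations are observed, about 15 CMHCs per package on average, and the descriptive answer for each package holds among the centres that chose it. Analysts will arrive at that denominator because no other can be computed.

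Neither bias nor a wrong decision on hypothesis 1 has been shown. The ranges above rest on an assumed 20% of choosers at benchmark, an assumed 10 to 20 choosers and a mean borrowed from another project. The chooser/non-chooser difference has no value in the protocol. Research question 2 compares the two chosen packages within each CMHC after randomization, so the choice does not impair its validity. Restating the scope for research question 1 would repeat what sections 2.2.3 and 2.3.4 already say and would alter no data, analysis or result.

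### Eight CMHCs per branch cannot be reached in all four packages (64 places needed, 60 available), so power for the package-level comparisons is not assured; the 30-pair analysis is unaffected

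*Protocol*

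**What the plan says.** Protocol section 2.2.3 (necessary number of CMHCs) states that "we need 8 CMHCs in each branch to show that implementation support for a treatment package gives a significant increase in fidelity", with the comparator described as "compared to baseline or low fidelity". The inputs come from a US implementation project: mean fidelity of "2.28 (SD 0.95) at baseline 3.76 (SD 0.78) after 12 months (effect size 1.70"). The section then says: "Our calculation is based on their data and 5% two-tailed significance and 90% power".

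The section on treatment packages for randomization (within 2.2.4) limits the study to four packages, partly "to obtain the necessary power for the statistical analyses (see calculations under 2.2.3 above").

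On the design, section 2.2.3 says "Each of the 30 CMHCs chooses two of packages that they will implement" and "For each center we randomize implementation support to one package and no support to the other one". No section sets a minimum number of CMHCs per package or balances support against no support within a package.

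Section 2.2.8 plans two between-condition analyses for research question 2. The first pools the 30 pairs and ignores which package is involved. The second compares supported with unsupported sites within each package. Both use baseline fidelity as a covariate. The section acknowledges that the size of the second analysis depends on what the centres choose.

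**The concern.** The requirement of 8 per branch is worded for a single package, and the limit of four packages is then presented as securing it. If the design cannot place 8 CMHCs in each branch of each package, that justification fails for the package-level comparisons. A package that shows no significant effect could then be read against an assumed 90% power that its comparison did not have, and support for that package might be judged ineffective on too little information.

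**Working it through.** **1. Reproduce the protocol's figure.** Inputs from section 2.2.3: means 2.28 and 3.76, SDs 0.95 and 0.78.
- Difference: 3.76 − 2.28 = 1.48.
- Pooled SD: √((0.95² + 0.78²)/2) = 0.869.
- Effect size: 1.48/0.869 = 1.70, as stated.
- Normal formula for two groups: n = 2 × ((1.960 + 1.282)/1.70)² = 7.27, rounded up to 8 per branch. This matches.

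Power at 8 v 8 is 92.5% by the normal formula and 88.5% by the noncentral t distribution.

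**2. Count the places.** Needed: 4 packages × 2 branches × 8 = 64. Available: 30 CMHCs × 2 packages = 60, a mean of 15 per package. No pattern of choices or allocation gives all four packages 8 per branch. This step needs no power model.

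**3. Power with 15 CMHCs in a package** (effect size 1.70, two-sided 5%, no covariate). Noncentrality is 1.70 × √(n₁n₂/(n₁+n₂)), with n₁+n₂−2 degrees of freedom.

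| Split | t test | Normal formula |
|---|---|---|
| 8 v 8 (16 sites) | 88.5% | 92.5% |
| 8 v 7 | 85.9% | 90.7% |
| 9 v 6 | 84.6% | 89.7% |
| 10 v 5 | 81.8% | 87.4% |
| 11 v 4 | 76.8% | 82.9% |
| Average over Binomial(15, 0.5) splits | 83.2% | 88.5% |

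On the t basis, the fall from 90% to 83.2% breaks down as follows:
- t distribution instead of normal: 90 − 88.5 = 1.5 points
- 15 sites instead of 16: 88.5 − 85.9 = 2.6 points
- chance imbalance: 85.9 − 83.2 = 2.7 points (2.6 before rounding)

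**4. Add the planned baseline covariate.** The protocol gives no correlation between baseline and follow-up fidelity, so r is an assumption. The effect size becomes 1.70/√(1−r²), with one degree of freedom fewer. Average power over chance splits of 15 is 82.7% at r = 0, 86.0% at 0.3, 88.5% at 0.4 and 91.6% at 0.5.

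**5. Vary the uptake** (averaged over chance splits, t test).

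| CMHCs choosing the package | Unadjusted | Adjusted, r = 0.5 |
|---|---|---|
| 10 | 61% | 71% |
| 12 | 72% | 82% |
| 15 | 83% | 92% |
| 18 | 91% | 96% |
| 20 | 94% | 98% |

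The total is fixed at 60, so a gain for one package is a loss elsewhere. If one package has 18, the other three average (60 − 18)/3 = 14.

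**6. The first analysis.** For 30 pairs at a difference of 1.48 and zero within-pair correlation, the standardised paired difference is 1.48/(√2 × 0.869) = 1.20, and power exceeds 99.9%. The 30 pairs give about 90% power for a standardised paired difference of 0.61.

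**7. Effect of blocking.** Four packages form six possible pairs. Suppose 5 CMHCs choose each pair and each block of 5 splits 3:2, the direction being random. Each package belongs to three blocks, so it has 6 to 9 supported sites out of 15, and its smaller branch is never below 6. The split is 9 v 6 with probability 1/4 and 8 v 7 with probability 3/4. Average unadjusted power is ¼ × 84.6% + ¾ × 85.9% = 85.6%. Under coin-flip allocation with the same choices, simulation puts the chance that at least one package has a branch of 5 or fewer at about 69%.

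**The case against.** The strongest reply is that the protocol's 8 is a rounded-up 7.27. Unrounded, the need is 4 × 2 × 7.27 = 58.2 places, so 60 suffice by the protocol's own formula when splits are balanced (90.7% at 8 v 7). That is correct: the four-place shortfall alone does not take power below 90% on that basis. But balanced splits and equal uptake are exactly what the protocol does not fix.

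The planned baseline adjustment could also restore about 92%. This stands as a possibility at an assumed correlation of 0.5, which the protocol neither states nor supports with data. Section 2.2.8 is open about the dependence on centres' choices, section 2.2.3 warns that smaller differences would need a larger sample, and a May 2015 survey is said to have shown adequate interest in the four packages. No counts from it are given, and these remarks do not fit easily with the assurance in section 2.2.4.

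Two stronger readings are tempting. A reader might infer that unbalanced randomisation is what pulls power down to 83%. The documents do not support this: imbalance accounts for about 2.6 points, and 83% holds only for an unadjusted t test, equal uptake and unrestricted allocation. A reader might also infer that the trial is underpowered for research question 2. It is not, on its own assumptions: the main design is the paired comparison of 30 CMHCs, which has ample power at a difference of 1.48.

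**Conclusion.** The point holds for the package-level comparisons only. It is certain, by counting, that 8 per branch cannot be met in all four packages. It is also clear from the text that neither uptake nor balance within a package is controlled, so the claim that stopping at four packages obtains the necessary power is not supported for those comparisons.

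The size depends on assumptions. With equal uptake the loss is modest and could vanish with a useful baseline covariate. With 10 CMHCs in a package, power is well short of 90% whether unadjusted or adjusted at a correlation of 0.5. All these figures take the effect size of 1.70 as given. The matter should be corrected, but it does not threaten the main comparison.

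**What to change.** 1. In sections 2.2.3 and 2.2.4, say that 8 per branch at 90% power is not assured for each package. Give package-level power as a range over uptake and an assumed baseline correlation, using the step 5 figures or similar. State the power of the 30-pair analysis as the basis of the design: about 90% for a standardised paired difference of 0.61.

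2. Randomise support in blocks within the six possible package pairs. Section 2.3.4 places package choice in November/December 2015 and randomisation after the baseline assessment, so all choices are known in time. With equal choices this raises average unadjusted power from about 83% to about 86% and rules out any branch of 5 or fewer. With unequal choices it still keeps the two branches of a package within three sites of each other, because each of its three blocks can be uneven by at most one. Blocking does not cure low uptake, which is why the range in item 1 is needed.

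The cost is wording, a blocked allocation list and a less favourable stated figure for the package-level analysis. No extra CMHCs are needed, and the within-centre pairing is kept.
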